### **2.1.2 Unadjusted association of treatment assignment and outcomes**

After checking for balance across patient characteristics, we shall estimate treatment-outcome associations assuming binary outcomes

#### **2.1.2.1 Relative risks**

Stratified (by site and language) Mantel Haensel

Estimates = RR and confidence interval

Make a new variable that is the combination of site and language = l\_site

Stata: cs outcome treatment, by(l\_site)

This is a "fixed effects" analysis and does not consider the effect on variance of variation across sites in the effect of treatment (See section 2.4).

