### **Parent randomization**

Randomization will occur with a 1:1 allocation ratio stratified by:

- clinical site (such that each site will have a balance of intervention and usual care plus participants)
- child's age group (6-23 months vs. 2-8 years)
- parental language (English versus Spanish preference)

To ensure allocation concealment (a technique used to prevent selection bias), the CHOP/Penn statistician will prepare for each site a separate randomization list stratified by age and language, using randomly permuted blocks with varying block sizes.

If the parent is assigned to usual care, they will receive the existing influenza vaccination protocol for any given practice. This may include other forms of influenza vaccine reminders. In season 2, caregivers randomized to usual care will be sent a message upon enrollment containing a link to health and parenting information from the American Academy of Pediatrics website. If a parent is assigned to the intervention arm, we will follow the protocol under *Study Intervention: Text Messages*.

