## **Statistical Analysis Plan (SAP) – Flu2Text - v1.6**

### **Date of final SAP: September 12, 2019**

This plan, based on the original proposal and the IRB protocol, will guide analyses. It follows the aims outlined in the proposal. In keeping with recent guidance of the American Statistical Association, we will avoid statements about “statistical significance”. When reported, p-values will be continuous, unless they are below 0.001, when we shall use the notation “ $p<0.001$ ”, in keeping with general guidance on very small p-values. We shall report p-values with 2 decimal places if they are larger than 0.10 and to 3 decimal places otherwise. Point estimates and confidence bounds will be the primary means of reporting results and their precision. Primary analyses are reported below where indicated. Software tools are also listed, but are subject to modification if they fail to converge or produce results.

For overall guidance, we will follow those from [New England Journal of Medicine](#) (Last accessed, Sep 11, 2019).

We shall date this SAP upon agreement and completion and then date all amendments.

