### **2.1.1 Testing for balance from randomization based on patient-level covariates**

The initial check will be whether randomization produced balance of the sites and covariates. For this check, we will fit a model:

Outcome is treatment assignment. Logistic regression – with all covariates included.

1. Check that overall likelihood ratio statistic is not significant.
2. Suggests overall balance consistent with successful randomization.

Balance check covariates:

- time from 1st (initial) dose to randomization
- child age
- child gender
- text language
- child health insurance

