### 2.1.2.2 Binary outcomes – risk differences

Risk differences are important measures and should be reported along with relative risks. But standard packages do not report risk differences using Mantel Haenszel approaches. There are two alternatives that might be indicated.

*Alternative #1. Newcombe*

SAS: Alternative – Mantel Haenszel methods for risk difference with Newcombe confidence bounds.

Let "strata" be the combination of site and language.

```
PROC FREQ;  
Tables strata*treatment*outcome/riskdiff method=newcombe;  
Run;
```

*Alternative #2. Bohning (Biometrics 2000) - confirmatory*

Bohning proposed, and we have programmed in Stata, a Mantel Haenszel approach for estimating risk differences. We propose to use this as our primary approach and then to use Newcombe as a check on sensitivity. Both methods might be helpful because risk differences (stratified) are not as well-accepted as methods for stratified relative risk. This will be a secondary analysis only for purposes of confirmation.

Binary outcomes are (as noted above): Second dose status as of April 30 (primary), and as of day 42 from child's date of first dose (secondary).

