### 2.1.3 Analysis with covariates (if check on balance fails)

#### 2.1.3.1 Conditional logit models (likely not applicable owing to randomization)

Conditional logistic regression model, adjusted for covariates, stratified by site.

Stata: clogit outcome treatment covariates, group(site)

Compare with the model (covariate unadjusted) such as Mantel Haenszel approaches.

Stata: clogit outcome treatment, group(site)

Do the estimates of the effect of treatment differ between these two models? If yes, then some chance imbalance in covariates across treatment groups is imparting some bias in the unadjusted estimates.

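### Age group is a randomisation stratum but is missing from the strata of the Mantel-Haenszel relative risk and the stratified risk difference; the reported RR standard error is slightly too large if age group predicts completion

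*Combined protocol and SAP*

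**What the plan says.** Protocol, Parent randomization: allocation is 1:1, stratified by clinical site, "child's age group (6-23 months vs. 2-8 years" and parental language. Each site has a "separate randomization list stratified by age and language, using randomly permuted blocks with varying block sizes".

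SAP 2.1.2.1 gives the relative risk as "Stratified (by site and language) Mantel Haensel" and builds one variable, `l_site`, from those two factors. SAP 2.1.2.2 lets the risk-difference strata "be the combination of site and language". Neither section mentions age group or explains its absence.

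Child age does appear elsewhere:

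- **SAP 2.1.1** lists it in a logistic model of treatment assignment, where the instruction is "Check that overall likelihood ratio statistic is not significant".
- **SAP 2.1.3** brings covariates into the outcome model only if that check fails. The subsection is headed "Conditional logit models (likely not applicable owing to randomization" and the model is "clogit outcome treatment covariates, group(site".
- **SAP 3.0.1.1** lists age group as a candidate effect modifier under Aim 3, which section 3.0 calls exploratory.

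The SAP's opening section states: "Point estimates and confidence bounds will be the primary means of reporting results and their precision".

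**The concern.** Blocking on a factor holds it nearly equal between arms, so variation in outcome due to that factor no longer contributes to the true sampling error of the treatment comparison. A standard error computed in strata that ignore the factor still counts that variation, and the interval comes out too wide. Here two of the three randomisation factors reach the Aim 1 binary analysis and one does not. Since this SAP reports precision mainly through confidence bounds, their width matters more than usual.

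The fallback in 2.1.3 does not close the gap. A balance test asks whether chance imbalance occurred, whereas the issue is whether the standard error matches the design. Even if triggered, conditional logistic regression grouped by site gives an odds ratio, not an age-adjusted RR or risk difference. The Aim 3 analysis looks for effect modification and does not supply the main estimate.

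**Working it through.** The plan states no power, effect size or age-specific rate, so there is no figure of its own to reproduce.

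**Inputs from the documents.** Up to 4,000 parents over two seasons (Overview), hence about 2,000 per season; 40-50 sites; seasons analysed separately (SAP 2.0.1); 40-60% background second-dose completion (Background).

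**Assumed.** Age gaps in completion of 0, 10, 20 and 30 points; equal age groups; 20% Spanish with no language effect; control completion 47%; a constant 6-point effect; site SD 10 points; block sizes 2/4/6; two-sided 95% intervals.

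**1. Closed form.** With 1:1 allocation balanced on age and no treatment effect,

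reported SE / true SE = sqrt[ p(1-p) / Σ w_k p_k(1-p_k) ],

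where p is the pooled rate and w_k and p_k are the share and rate of age group k. With equal groups and p = 0.5:

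- 10 points (0.45, 0.55): sqrt(0.25/0.2475) = 1.005
- 20 points (0.40, 0.60): sqrt(0.25/0.24) = 1.021
- 30 points (0.35, 0.65): sqrt(0.25/0.2275) = 1.048

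**2. Simulation of the RR.** 45 sites × 44 parents = 1,980 per season, 10,000 seasons per gap. The planned analysis is the Mantel-Haenszel log RR with Greenland-Robins variance in site-by-language strata. The alternatives are (a) Poisson with site-by-language fixed effects, one age-group term and robust SE, and (b) Mantel-Haenszel with age added to the strata.

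| Age gap (points) | 0 | 10 | 20 | 30 |
|---|---|---|---|---|
| Planned: mean SE / true SD | 1.00 | 1.00 | 1.01 | 1.04 |
| Planned: coverage, % | 95.1 | 95.2 | 95.3 | 95.8 |
| (a) coverage, % | 95.1 | 95.2 | 94.9 | 95.1 |
| (a) change in reported SE, % | +0.1 | -0.4 | -1.7 | -4.1 |
| (b) change in reported SE, % | +0.5 | -0.1 | -1.6 | -4.2 |

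Monte Carlo error of a true SD is about 0.7%. A change of -4.1% means the planned SE is 1/0.959 = 1.043 times the adjusted one, close to the closed form. In a shorter run (800 seasons per gap), adding age to the strata moved the true SD by +0.3, +0.4, -0.6 and +0.8%, which is noise. What changes is the reported SE.

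A separate simulation (10-30% Spanish, 50-80% of children aged 6-23 months, true RR 1.0 to 1.15) gave an SE without age of 1.00 times the SE with age at 10 points and 1.01-1.02 times at 20. It showed no under-coverage and no bias.

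**3. Sensitivity of (a).** The gain shrinks with unequal age groups: a 70/30 split gives -1.5% at 20 points and -3.5% at 30; an 85/15 split gives -0.8% and -2.0%. With 40 sites of 20 parents the changes are +0.6% at no gap, -1.0% at 20 and -3.1% at 30. With 30% control completion (assumed for day 42) the change is -2.0% at 20 points.

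**4. Would the fallback open?** In 4,000 simulated seasons the five-covariate check failed in 1.1% at an assumed 5% level. The age-group likelihood ratio statistic never exceeded 1.27 against a critical value of 3.84. That maximum depends on coding: with age in months (500 seasons) the age Wald statistic reached 4.34, yet the overall check failed in 1.2% either way. Sites were not in the simulated check.

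**5. Risk difference, indicative only.** A linear fixed-effects model with age, compared with Mantel-Haenszel using Sato variance, changed the SE by +0.1, -0.4, -2.0 and -4.6%. The Böhning variance was not tested. In one implementation of a stratified Newcombe interval, adding age to the strata did not narrow it at 30 points (half-width/1.96 of 0.02256 against 0.02245).

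**6. Sparsity.** With 40-50 sites there are 80-100 site-by-language strata of 20-25 parents. Adding age gives 160-200 strata of 10-12.5. Children in one-arm strata rise from 0.4 to 10.8 of 1,980 (0.5%), to 16.5 (0.8%) with a 70/30 split, or from 9.6 to 34.5 of 800 (4.3%) with 20 per site. The least even mix tried (10% Spanish, 80% aged 6-23 months, 50 × 40) gave 35 of 2,000 (1.75%).

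**The case against.** The strongest reply is that nothing demonstrable goes wrong. Coverage holds, the error is on the conservative side, the estimator's real variability does not improve, and any cost needs an age gap that the documents nowhere report. SAP 2.1 prefers assumption-free methods where possible, 2.1.2 presents this as the unadjusted analysis, and coarser strata are a defensible guard against sparse cells.

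Most of that stands and limits the size of the point. It does not remove it. The SAP does not offer sparsity as its reason, and sparsity does not apply to a single age-group term on the existing strata. Reported precision is what the SAP says it will rely on, and matching it to the randomisation costs almost nothing.

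The objection also stands for the risk difference. SAP 2.1.2.2 calls Böhning its primary approach (while also labelling it confirmatory), so results from other variance methods cannot fix the cost there.

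A reader might infer more than the documents support:

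- **That the primary result is biased or its interval invalid.** Allocation is blocked on age, and no scenario showed bias or under-coverage from the omission.
- **That age is ignored altogether.** It is in the balance check and in Aim 3.
- **That the RR interval is therefore sound in every respect.** The check assumed a constant effect. SAP 2.1.2.1 itself sets aside variation in effect across sites, and this point says nothing about that.

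**Conclusion.** The mismatch between randomisation and analysis strata is certain from the text. Its consequence is small and conditional: an RR standard error too large by about 0% at a 10-point age gap, 2% at 20 and 4% at 30, less if the age groups are unequal. These figures rest on assumed gaps, on 1,980 parents per season and on a constant treatment effect. The conclusion covers the omission of age group from the binary analyses only. For the risk difference the direction is plausible but the size under the planned method is unknown, and nothing is claimed about the time-to-event analyses. This is a minor point of precision.

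**What to change.** For the RR at April 30 and day 42, account for age group regardless of the balance check, in one of two ways:

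- **One term.** A log-link (Poisson) model with site-by-language fixed effects, age group as a single covariate and robust SEs. If age is not prognostic, the reported SE rises by about 0.1% (0.6% with 20 parents per site). A regression model is less assumption-free than SAP 2.1 prefers, although coverage held at 94.9-95.2% here.
- **Finer strata.** Add age group to `l_site` where cells allow. The SE rises by about 0.5% if age is not prognostic (1.7% with 20 per site), and one-arm strata take up the small share of children shown above.

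For the risk difference, give an age-adjusted estimate from the linear fixed-effects model that SAP 3.1.1 already plans for subgroups, next to the planned estimate. Finer risk-difference strata are not advised unless the variance method is shown to hold in sparse cells.

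Report the planned Mantel-Haenszel estimates alongside and enter the change as a dated amendment in SAP section 5.0. The SAP is dated September 2019, after the second season ended. If outcomes by arm have already been seen, keep the planned analysis as primary and label the age-adjusted one a sensitivity analysis.

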### 2.1.2.2 Binary outcomes – risk differences

Risk differences are important measures and should be reported along with relative risks. But standard packages do not report risk differences using Mantel Haenszel approaches. There are two alternatives that might be indicated.

*Alternative #1. Newcombe*

SAS: Alternative – Mantel Haenszel methods for risk difference with Newcombe confidence bounds.

Let "strata" be the combination of site and language.

```
PROC FREQ;  
Tables strata*treatment*outcome/riskdiff method=newcombe;  
Run;
```

*Alternative #2. Bohning (Biometrics 2000) - confirmatory*

Bohning proposed, and we have programmed in Stata, a Mantel Haenszel approach for estimating risk differences. We propose to use this as our primary approach and then to use Newcombe as a check on sensitivity. Both methods might be helpful because risk differences (stratified) are not as well-accepted as methods for stratified relative risk. This will be a secondary analysis only for purposes of confirmation.

Binary outcomes are (as noted above): Second dose status as of April 30 (primary), and as of day 42 from child's date of first dose (secondary).

### 2.1.3 Analysis with covariates (if check on balance fails)

#### 2.1.3.1 Conditional logit models (likely not applicable owing to randomization)

Conditional logistic regression model, adjusted for covariates, stratified by site.

Stata: clogit outcome treatment covariates, group(site)

Compare with the model (covariate unadjusted) such as Mantel Haenszel approaches.

Stata: clogit outcome treatment, group(site)

Do the estimates of the effect of treatment differ between these two models? If yes, then some chance imbalance in covariates across treatment groups is imparting some bias in the unadjusted estimates.

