## 2.1 Analysis – binary outcomes – primary analysis and outcome

Outcome = Receipt of the second dose of influenza vaccine, a binary outcome.

By April 30, the end of the season - primary

By Day 42 from the day of first dose - secondary

Formal question to be answered: "If a group of children were alternatively assigned to the two treatment arms, what would be differences in completion of influenza vaccines by the end of the season, defined as April 30th of each season?"

The alternative and secondary endpoint will evaluate receipt of the second dose as of day 42 from the date of the child's first dose.

Randomization, if successful, should lead to exchangeability of two groups and permits estimation of the treatment differences (as the control group should be the same as the intervention group).

Preliminary analysis of time from the first dose to time of randomization showed no difference between intervention and control groups, and reflects successful randomization. This analysis was conducted as part of assessing balance and without regard to outcomes.

Primary analyses will proceed where possible with assumption-free methods. Dropout was negligible and so adjustment for dropout was not needed nor specified in the final SAP.

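### Section 2.1.3.1 reads any change in the odds ratio after covariate adjustment as bias from imbalance, which does not follow; separately, the Aim 1 strata omit age group, a randomisation factor (minor)

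*Combined protocol and SAP*

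**What the plan says.** SAP section 2.1.1 regresses treatment assignment on five covariates (time from first dose to randomisation, child age, gender, text language, insurance) and instructs: "Check that overall likelihood ratio statistic is not significant". Section 2.1.3 applies only if that check fails, and the heading of 2.1.3.1 adds "likely not applicable owing to randomization".

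If it is reached, 2.1.3.1 fits a conditional logit with covariates, grouped by site, and then says "Compare with the model (covariate unadjusted) such as Mantel Haenszel approaches". The code line given for this second model is also a conditional logit grouped by site. The section asks whether the treatment estimates of the two models differ, gives no threshold, and concludes: "If yes, then some chance imbalance in covariates across treatment groups is imparting some bias in the unadjusted estimates". It does not list the covariates.

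The primary Aim 1 analysis is on another scale. Section 2.1.2.1 gives a relative risk, "Stratified (by site and language) Mantel Haensel", and 2.1.2.2 adds "Risk differences are important measures and should be reported along with relative risks", using the same site-by-language strata. The protocol (Parent randomization) stratifies allocation by site, language and "child's age group (6-23 months vs. 2-8 years"). Age group is in the balance check and among the exploratory Aim 3 modifiers, but not in the Aim 1 strata, and no reason is given.

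**The concern.** The rule treats a change in a conditional odds ratio as a measure of confounding by chance imbalance. In a logistic model that change has two parts. One is the effect of imbalance. The other is non-collapsibility: conditioning on a prognostic covariate moves the odds ratio away from 1 even when the arms are perfectly balanced on it. The rule assigns both to imbalance. A sound unadjusted result could then be reported as biased or, where a little imbalance is real, the bias could be read in the wrong direction.

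This design makes the second part relevant. Age group and language are balanced by the stratified randomisation, so if they enter the adjusted model, the change they cause is almost all non-collapsibility.

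The omission of age group from the Aim 1 strata is a separate matter. It bears on interval width, not on bias.

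**Working it through.** The plan gives no effect size, covariate strength or threshold here, so there is no figure to reproduce.

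**Inputs.** From the documents: control risk 40–60% (protocol Background); up to 4,000 parents over two seasons (Overview); at least 40 parents per practice per season (Practice inclusion criteria). Assumed: treatment odds ratio 1.5; binary covariates split 50/50; covariate odds ratios 1.5–5; an equal split between seasons, hence 4,000 / 2 / 2 = 1,000 per arm.

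**Step 1: perfect balance, one covariate.** Choose control risks in the two covariate levels that average to the control risk, multiply each odds by 1.5, and average the text-arm risks. Take control risk 50% and covariate odds ratio 3:
- Control risks 0.366 and 0.634, odds 0.577 and 1.732.
- Text-arm odds 0.866 and 2.598, risks 0.464 and 0.722, mean 0.593.
- Unadjusted odds ratio (0.593/0.407)/(0.5/0.5) = 1.458, against 1.500 adjusted. Rise: 1.500/1.458 − 1 = 2.9%.
- The relative risk (1.186) and risk difference (9.3 points), standardised over the same covariate mix, equal the unadjusted values exactly.

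| Covariate OR (control risk 50%) | Unadjusted OR | Adjusted OR | Rise | RR and RD |
|---|---|---|---|---|
| 1.5 | 1.494 | 1.500 | 0.4% | unchanged |
| 2 | 1.482 | 1.500 | 1.2% | unchanged |
| 3 | 1.458 | 1.500 | 2.9% | unchanged |
| 5 | 1.415 | 1.500 | 6.0% | unchanged |

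At control risk 40% the range is also 0.4–6.0%; at 60% it is 0.4–5.4%. Overall this is 0.04–0.65 standard errors of the log odds ratio at 1,000 per arm.

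**Step 2: real imbalance.** Control risk 50%; age group (odds ratio 3) balanced; favourable insurance category (odds ratio 2) held by 52.5% of the text arm and 47.5% of controls.
- Risks averaged over age, by insurance level: text 0.5137 and 0.6683; control 0.4202 and 0.5798.
- Text: 0.475 × 0.5137 + 0.525 × 0.6683 = 0.5948. Control: 0.525 × 0.4202 + 0.475 × 0.5798 = 0.4960.
- Unadjusted risk difference 9.88 points; with balance, 59.10 − 50.00 = 9.10. The unadjusted effect is overstated.
- Unadjusted odds ratio (0.5948/0.4052)/(0.4960/0.5040) = 1.492. Adjusting for age and insurance gives 1.500. The rise suggests the effect was understated, which is the wrong direction.
- At 6 points of imbalance the odds ratio goes from 1.501 to 1.500, the correct direction. Adjusting for insurance alone at 5 points gives 1.492 to 1.459, also correct.
- A single unbalanced covariate can still mislead at a smaller imbalance. With odds ratio 3 and 2 points, the odds ratio rises from 1.489 to 1.500 although the unadjusted value exceeds its balanced value of 1.458. At 3 points (1.505 to 1.500) the direction is right.

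**Step 3: age group in the strata.** Simulated seasons (assumed: 50 sites × 40, 20% Spanish, 60% aged 6–23 months) give these changes in risk-difference interval width when age is added to site × language:

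| Age OR | 1 | 1.5 | 2 | 3 | 5 |
|---|---|---|---|---|---|
| Change in width | +0.6% | +0.1% | −0.7% | −2.7% | −6.2% |

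Hand check for odds ratio 2, ages split evenly: the share of variance explained by age is 0.0858²/0.25 = 0.029 in controls and 0.0825²/0.2406 = 0.028 in the text arm, about 0.029. Sparse strata cost about 1.2% of the weight. √(1 − 0.029) / √(1 − 0.012) = 0.991, or about −0.9%, close to the simulated −0.7%.

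A separate simulation (25 sites × 40, true relative risk 1.15) gives mean estimates of 1.150–1.153 without age strata and 1.150–1.152 with them. With a 30-point age gap in uptake, the model standard error falls from 0.0593 to 0.0565, while the actual spread barely changes (0.0547 to 0.0544). The stratified randomisation has already delivered the precision; the coarser strata do not report it.

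**The case against.** The strongest reply is that little depends on this sentence. It applies only after a failed balance check. In simulation under the assumed inputs, with a 0.05 level that the SAP does not state, the check failed in 459 of 32,401 seasons (1.4%). In those seasons the odds-ratio change did track the realised bias (correlation 0.83–0.95), so it is not uninformative. That stands, and it limits the weight of the point. It does not make the inference valid.

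A reader might infer that the rule generally points the wrong way. The documents do not support that. Section 2.1.3.1 does not list its covariates, and section 2.3.5, on restricted mean survival time, speaks of adjusting for the covariates that are out of balance. On that reading the direction in the 5-point example is correct. The wrong direction there needs a strong, balanced covariate in the model and only a small imbalance, and the shift (1.492 to 1.500) is about 0.06 standard errors at 1,000 per arm.

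A reader might also take the mention of Mantel-Haenszel to mean that an odds ratio is to be compared with a relative risk. The wording is loose, but the two code lines are parallel conditional logits, and the question that follows concerns those two models. The natural reading is odds ratio against odds ratio.

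On age group, it can be said that coarser strata avoid sparse cells, in keeping with the aim in SAP section 1.0 of avoiding small categories, and that the gain is nil if age barely predicts uptake. Both are fair.

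**Conclusion.** The inference in section 2.1.3.1 is incorrect as written: a difference between the two odds ratios does not by itself show imbalance bias. Under perfect balance the shift is 0.4–6.0%, given an assumed treatment odds ratio of 1.5 and covariate odds ratios of 1.5–5. At small imbalances the direction can be wrong; at larger ones it is right.

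Severity is minor. A reader might conclude that the primary result is at risk, but the SAP nowhere lets this odds ratio replace the Mantel-Haenszel relative risk or risk difference, and both remain valid.

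The age-group omission is a mismatch between design and analysis. It causes no bias, and the intervals are slightly wide if age predicts uptake. The documents give no age effect, so the range of about +0.6% to −6% in width rests on assumed age odds ratios of 1 to 5.

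**What to change.** Delete the sentence that infers bias from a difference. If an adjusted result is shown, report it as a supportive standardised relative risk and risk difference, and compare it with the unadjusted result on that scale only. This needs no new data.

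For Aim 1, define the Mantel-Haenszel strata as site × language × age group in each season, and keep the site × language result alongside. This remains model-free and fits the SAP's own preference: "Primary analyses will proceed where possible with assumption-free methods".

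The SAP is dated September 2019 and season 2 ended in April 2019. The change should therefore be a dated entry in section 5.0 that states whether outcomes had been examined.

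The cost is one changed stratum variable and some weight lost to strata with only one arm: about 1.2% at 40 per site, 3.4% at 20 and 7.7% at 10 in the simulations. At 20 per site the change in width runs from +1.7% to −4.9%, so small sites gain less.
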